Multiple imputation may become necessary if there is substantial missing (>5%), which will yield insufficient power in the final models. The risk of this is present because the outcome measures used in the models require the participants to have valid answers at both 6 and 12 months. If multiple imputation of outcome becomes necessary, it will be performed on the outcome's original scale, before dichotomizing the outcomes and combining the time points. We will use all predictors and auxiliary variables in the multiple imputation models to reduce bias introduced in the models. Observed and imputed values will be compared in tables and plots, and convergence will be checked. Number of imputations needed is dependent on if convergence is reached, and percentage of participants with missing values (22, 23).

Analyses

Descriptive statistics:

Descriptive data will be reported for both the development and validation sample, using mean and standard deviation for normally distributed continuous variables, median and interquartile range for continuous variables with skewed distribution, and with frequency and proportions for categorical variables. Normal distribution will be examined visually using histogram and QQ-plot, and statistically with the Shapiro-Wilk test.

The proportion of patients with non-recovery will be presented for each outcome for the development and validation samples.

Loss-to-follow-up and dropout will be counted and assessed. Reasons for such will be presented where available. Patients withdrawing their informed consent during follow-up will not be included in the analyses. The baseline characteristics of patients lost to follow-up will be compared to those remaining in the study.

External validation:

We will follow the three steps outlined by Debray et al (24) when assessing external validity:

Step 1, sample relatedness:

Sample relatedness will be assessed by comparing the patient characteristics in the validation sample to the development sample. We will assess each characteristic separately, using summary measures like percentage, mean and standard deviation, or median and range. (Table 3 below.)

Step 2, external validation performance:

The models tested in the external validation sample looks as follows:

Persistent back pain = $-4.23 + 0.03 \cdot \text{Age} + 0.73 \cdot \text{Chronic duration} + 0.23 \cdot \text{Back pain intensity} + 0.07 \cdot \text{Disability} + 0.71 \cdot \text{Recent episode} + 0.38 \cdot \text{Spinal morning stiffness} + 0.42 \cdot \text{Pain during spinal rotation} - 0.79 \cdot \text{Recovery expectation}$

Persistent disability = $-5.97 + 0.04 \text{Age} + 0.63 \text{Chronic duration} + 0.32 \text{Disability} + 0.40 \text{Recent episode} + 0.52 \text{Comorbidity} + 0.52 \text{Spinal morning stiffness} - 0.83 \text{Recovery expectation} + 0.08 \text{Depressive symptomology} + 0.02 \text{Pain catastrophizing}$

Persistent self-reported non-recovery = $-3.46 + 0.03 \text{Age} + 0.60 \text{Chronic duration} + 0.13 \text{Disability} + 1.11 \text{Recent episode} + 0.36 \text{Pain during spinal rotation} - 0.95 \text{Recovery expectation}$

Model performance will be measured with calibration-in-the-large (CITL), calibration slope, Nagelkerke's pseudo- R^2 , and Area under Receiver Operator Characteristics curve (AUC). (Table 4 and Figure 1 below.) CITL and calibration slope is assessed through a calibration plot, where observed outcomes are plotted against predicted risks. Perfect calibration is indicated by a CITL value of 0 and a calibration slope value of 1 (14). Nagelkerke's pseudo- R^2 is a measure of overall model performance that ranges between 0 (worst possible performance) and 1 (best possible performance). AUC is a measure of the model's discriminative performance. A value of 1 indicates perfect discrimination and a value of 0.5 indicates discrimination no better than chance. AUC values between 0.7 and 0.8 are considered acceptable, between 0.8 and 0.9 excellent, and between 0.9-1.0 outstanding (25).

Step 3, model recalibration and updating:

If the models perform unsatisfactorily in the validation sample, updating the models may be needed. We will assess several alternatives in a step-by-step manner during this stage, following the frameworks of Debray et al (24) and Steyerberg (14):

1. Adjustment of model intercept, in case of poor calibration-in-the-large.
2. Overall adjustment of the calibration slope, in case of poor calibration slope.
3. In case of poor discrimination in validation models compared to original models, model revision may be performed. This involves re-estimation of predictor effects, including assessing linearity assumptions of continuous prognostic factors with restricted cubic splines or fractional polynomials. The re-estimated predictor effects will be corrected for over-optimism by applying a uniform shrinkage factor derived from 500 bootstrapped samples.
4. Model extension, introducing new candidate predictors to the model and assess improvement in performance. The candidate predictor to be tested and rationale can be found in Table 2 below.

Table 2: Candidate prognostic factor for model extension.

Candidate prognostic factor	Rationale
Reduced sleep quality attributable to back pain (based on item 5i from PSQI)	Sleep problems are common in older adults (26), and associated with disability in a cross-sectional study on back pain in older adults (27). Reduced sleep quality often co-occurs with chronic pain (28-30).
PSQI: Pittsburgh Sleep Quality Index	

If model performance after completing a step is acceptable, we will not proceed with further steps.

Sensitivity analyses

Complete case analyses will be performed to assess the possible bias introduced from the imputation procedure.

Proposed tables and figures

Baseline characteristics:

Table 3: Patient characteristics and clinical status at baseline in development sample and validation sample.

	Development sample, BACE-D		Validation sample, BACE-N	
	All participants (n=675)	Missing, n (%)	All participants (n=452)	Missing, n (%)
Age, mean (SD)				
Female, n (%)				
BMI, mean (SD)				
Education level high, n (%)				
Employment status currently paid work, n (%)				
Health-related quality of life (SF-36), mean (SD)				
Physical component score				
Mental component score				
Current smoker, n (%)				
Musculoskeletal comorbidity, n (%)				
One or more comorbidities, n (%)				
One or more previous back pain episodes, n (%)				
Recent episode of back pain, n (%)				
Radiating leg pain, n (%)				
Using pain medication, n (%)				
Sleep problems weekly due to back pain, n (%)				
Average back pain intensity last week (NRS, 0-10), mean (SD)				
Disability (RMDQ, 0-24), mean (SD)				
Duration of current episode > 3 months, n (%)				
Kinesiophobia (FABQ-PA, 0-24), mean (SD)				
Depression (CES-D, 0-60), mean (SD)				
Pain catastrophizing (PCS, 0-52), mean (SD)				
Expectations of being fully recovered or much better from back pain within next 3 months, n (%)				
Spinal morning stiffness more than 30/60 minutes ^a , n (%)				
Pain with active rotation of the back, n (%)				

SF-36, Short Form health survey 36; AUDIT-C, alcohol use disorders identification test, score ≥ 3 for women and ≥ 4 for men; NRS, numeric rating scale; RMDQ, Roland-Morris Disability Questionnaire; FABQ-PA, Fear-Avoidance Beliefs Questionnaire – Physical Activity; CES-D, Center for Epidemiological Studies – Depression; PCS, Pain Catastrophizing Scale; BBQ, Back Beliefs Questionnaire; TUG, Timed Up-and-Go.

^aDuration of morning stiffness was set at 30 minutes in BACE-D, and 60 minutes in BACE-N.

Table 4: Performance measures of external validation (This table will be provided for both the original models, and for updated/extended models)

Persistent back pain ($\geq 3/10$ on NRS at both 6 and 12 months)

Aspect	Measure	Value
Overall performance	Nagelkerke pseudo- R^2	
Discrimination	Area under the Curve	
Calibration	Calibration in-the-large	
	Calibration slope	

Persistent back-related disability ($\geq 4/24$ on RMDQ at both 6 and 12 months)

Aspect	Measure	Value
Overall performance	Nagelkerke pseudo- R^2	
Discrimination	Area under the Curve	
Calibration	Calibration in-the-large	
	Calibration slope	

Persistent non-recovery ($\geq 3/7$ on GPE at both 6 and 12 months)

Aspect	Measure	Value
Overall performance	Nagelkerke pseudo- R^2	
Discrimination	Area under the Curve	
Calibration	Calibration in-the-large	
	Calibration slope	

[figure not shown]

Figure 1: Calibration plot from Traeger et al (8). Calibration plots will be shown for the models tested in Step 2, and for possible updated and/or extended models (Step 3).

References

TSD	Services for Sensitive Data (Tjeneste for Sensitive Data)

Signatures

[name],
main author of the SAP

[name],
senior statistical advisor

[name]
principal investigator

2. Background and objectives

Background

Back pain represents a considerable burden on the society as well as the individual (1–6) and most people will experience back pain at some point during their life (7). Among older adults, low back pain (LBP) is the most common health problem that results in considerable disability (8,9). Many people seek primary health care for their back pain, and those aged 65 years or older is the second most common age group to visit physicians for LBP (10).

Back pain is recognized to be an episodic condition, with periods of flare-ups and (partly) recovery (11). The condition is highly heterogeneous in its presentation and course, and consequently, challenging for clinicians and patients to predict outcome and to decide on the best available treatment. Further knowledge on the clinical course of back pain in the older patients may provide a better understanding of the variability of recovery. Repeated measurements in cohort studies across different settings and countries have identified common back pain trajectory patterns, reflecting the heterogeneity of back pain course across individuals of different age groups (11–14). Previous evidence shows that for back pain trajectory studies, most studies have identified between 4 and 5 trajectory patterns for back pain: some differing mainly in terms of severity and less in the course patterns, and some differing in the course patterns (i.e., non-parallel and crossing trajectory lines) (for review see (11)). Further, the review showed that all studies identified a pattern of recovery (except one study that included only LBP patients with at least three months duration) and a pattern of persistent severe LBP (except one study excluding patients with unchanging pain due to their analytic approach). Moreover, patterns of more fluctuating pain, i.e., alternating LBP intensity and/or by LBP episodes with periods of no pain were observed (11). However, all included studies in the review excluded back pain patients >65 years of age.

Recently, some information in older adults have presented, with two large prospective cohort studies investigating the course of back pain in older adults. One found that half of the patients reported clinically important improvement in back pain intensity, but only 43% showed clinically important improvement in back-related disability after 2 years (15). 17% reported no back pain and no back pain-related disability at 2 years. The other found that 43% of older adults presenting to primary care with back pain reported themselves as (almost) recovered after 5-years (16). Moreover, what is considered as clinical improvement may not be as important for the patients. Perhaps adding an element of symptom satisfaction ought to be investigated to assess the patient's perspective on their own condition. One such was to investigate this is by using the

Patient Acceptable Symptom State (PASS) (17). Hence, this outcome will also be important to explore further and will be included in the present paper.

This study will build on a latent class analysis (LCA) performed on baseline data (cross-sectional) from this study population (ref/not published yet). The LCA found four classes based on Numeric Rating Scale (NRS), Self-Administered Comorbidity Questionnaire (SCQ), Roland-Morris Disability Questionnaire (RMDQ), Fear-Avoidance Belief Questionnaire (FABQA), Back Beliefs Questionnaire (BBQ), Center for Epidemiological Studies Depression (CES-D), and Pain Catastrophizing Scale (PCS). These four classes were named “The Positive”, “The Fearful”, “The Negative”, and “The Hopeful”. The first class (“The Positive”) had the overall lowest score for reported pain intensity, disability, comorbidities, symptoms of depression and pain catastrophizing. The second class (“The Fearful”) had the highest score on fear avoidance behaviour and comorbidity, with the second highest score on reported pain intensity, disability, catastrophising, and symptoms of depression. The third class (“The Negative”) had the highest score on most of the measurements. Of all the classes they showed the highest pain intensity, disability, symptoms of depression, and pain catastrophising. Moreover, class 3 had the second highest score on both reported comorbidities and fear avoidance behaviour. The fourth and final class (“The Hopeful”) had the second lowest overall score on all measurements. Unlike class one they had somewhat higher scores on pain intensity, disability, fear avoidance behaviour, symptoms of depression, and pain catastrophising.

Exploring the clinical course of back pain intensity and patient acceptable symptom state based on uncovered latent classes may add prognostic value and eventually contribute to better targeting the treatment of these patients.

Objectives

The primary aim is to explore the 2-year clinical course of back pain and symptom satisfaction among older adults seeking primary health care based on classes identified by latent class analysis.

3. Study population, design, and method

Study population and recruitment

Eligible patients for the BACE-N study were all people aged 55 years or older seeking primary care (general practitioner, physiotherapist, or chiropractor) with a new episode of back pain. A new episode was defined as being preceded by 6 months without visiting a primary care provider for similar complaints. Patients were excluded from the study if they had a cognitive impairment

which precluded them from completing the study questionnaires or if they had difficulties speaking and writing Norwegian. Patients who had severe mobility impairments (e.g., were wheelchair bound) were excluded if they could not complete the physical examination. While the study was ongoing, patients received care as usual.

Between April 2015 and February 2020 patients were recruited from general practitioners, physiotherapists, and chiropractors working in Norwegian primary care. Several of these practices were multidisciplinary clinics.

After completion of the initial clinical examination and questionnaire, patients were given follow-up questionnaires through email or postal mail at 3 months, 6 months, 12 months, and 24 months. The participants were informed that they may withdraw from the study at any time without any explanations or consequences.

Study design and setting

This study is using longitudinal data from an observational cohort study with a 2-year follow-up in a Norwegian primary care setting.

BACE-N is part of an international consortium. Details of the BACE-N are provided in the BACE-N protocol (ClinicalTrials.gov identifier: NCT04261309).

Variables

Outcome measure

The first outcome is average pain intensity during the last week (18,19) measured by the Numeric Rating Scale (NRS, 0 = no pain - 10 = worst pain imaginable). NRS is a subjective measure for pain (20), which is found to be preferable for low back pain cases (21).

The second outcome is symptom satisfaction (17). PASS consists of a single item: "How satisfied would you be if your current symptoms were to persist the rest of your life?", measured using a 5-point likert scale at 3 months, 6 months, and 1- and 2-year follow-up. The categories are "very satisfied", "somewhat satisfied", "neither satisfied nor dissatisfied", "somewhat dissatisfied" and "very dissatisfied".

Prognostic factor - Latent classes

A latent class analysis, currently in progress, will be used to identify the number of classes intended as prognostic factors in this analysis. The hypothesis is that there may be a difference in the clinical

course of the chosen outcomes depending on the probability of belonging to the different latent classes mentioned above.

Potential confounding factors

In line with the PROGRESS framework and recommendations for type 2 studies (22), we will adjust for confounding factors. Confounding factors included in the analysis, based on previous literature, related to pain intensity and symptom satisfaction are age (12,15,23), gender (12,24), educational level (25,26), employment status (still in paid work), and visited primary health care practitioner (27) (see table 1).

4. Statistical principles

Statistical analysis

All analyses described in this plan are considered *a priori* in that they have been defined in the protocol and/or in this SAP. In case they will be conducted, all post *hoc* analyses will be identified as such in the article. Further, all analyses will be carried out by the main author of this SAP using the STATA (StataCorp, College Station, TX, USA) or R.

To assess for normality of the variables of interest Q-Q plots and histograms will be used. Normally distributed data will be described using mean and standard deviation for continuous variables and counts and percentage for categorical data. Skewed data will be presented with medians and interquartile ranges.

Two separate analyses will be conducted for the two chosen outcomes. To investigate the association a general linear mixed model (GLMM) will be conducted to investigate the clinical course of both outcomes within the latent classes for all follow-up time points. GLMM is a regression-based technique which takes into account the dependency of the repeated observations of each individual, by adjusting for the correlations in estimating a variance for the intercept, a variance for the slope(s) or through different residual matrices (28). Both the unadjusted and the adjusted model will include the main effect of the classes and the follow-up time points, in addition to the interaction between the two (classes x follow-up). The adjusted model will include the selected covariates mentioned in section 3 (other variables). We will use a subject-specific random intercept.

Description of study flow

The flow of participants throughout all follow-up points will be visualized using a flow chart (see figure 1).

Participant characteristics

Baseline characteristics of eligible patients will be presented as shown in table 1.

Handling of missing data

Dataset including missing values will be used for the GLMM analyses, with no imputations for missing data (29).

Model estimation and selection

Model fit of GLMM will be assessed by comparing the log likelihood values and/or model fit statistics as Akaike Information Criterion (AIC) of neighboring [nested] models to determine whether the inclusion of a random slope is necessary and improves the model fit.

The results will be presented as crude and adjusted beta coefficients (B) with 95% confidence intervals (CI) as shown in table 2 and as margin plots with pairwise comparisons.

Sample size

This study contains secondary analyses embedded in the BACE-N study. The BACE-N study included a total of 452 participants which is deemed as an appropriate number of people for such a study (30). The number of subjects included for each time point (baseline, 3-, 6-, 12-, and 24 months) that answered all questions of interest in relation to the pain intensity analysis was 358, 306, 293, 281, and 248, respectively. In regard to the PASS investigation, these numbers for the same timepoints were 365, 295, 279, 272, and 230, respectively.

5. Presentation of the results

Table 1. Patient Characteristics at baseline based on classes identified by LCA (n =)

	Class 1	Class 2	Class 3	Class 4
Age (mean (SD))				
Gender (n (female))				
Education (n (%))				
Less than High School				
High School				

Higher education <4 years

Higher education > 4
years

Paid work (n (%))

Yes

No

Primary health care

practitioner (n (%))

General practitioner

Physiotherapist

Chiropractor

Pain intensity (NRS)

(mean (SD))

Symptom satisfaction

(PASS) (mean (SD))

SD – standard deviation, n – number, NRS – numeric rating scale, PASS – patient acceptable symptom state

Table 2. Estimates of fixed effects parameters from linear mixed models. Showing the association between latent classes, pain intensity (NRS) and symptom satisfaction (PASS) over 24 months.

	NRS score			PASS score		
	B	95% CI	P	B	95% CI	P
Unadjusted model						
Follow-up time points						
Baseline (ref)						
3 months						
6 months						
12 months						
24 months						
LCA class						
The Positive (ref)						
The Fearful						
The Negative						
The Hopeful						
Interaction Time x LCA						
Baseline x The Positive (ref)						
3 months x The Fearful						

3 months x The Negative

3 months x The Hopeful

6 months x The Fearful

6 months x The Negative

6 months x The Hopeful

12 months x The Fearful

12 months x The Negative

12 months x The Hopeful

24 months x The Fearful

24 months x The Negative

24 months x The Hopeful

Full model

Follow-up time points

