According to the STRATOS initiative task force, a complete prespecifying of all aspects in model building is unrealistic in observational studies (24). Thus, the following will provide a framework for analysis and model building in this study, not a detailed recipe. Decisions regarding final choice of models will be made by the first author, the advisory statistician and the principal investigator.

Primary aim, clinical course of back-related disability:

Mixed models for repeated measures will be used to account for statistical dependencies. RMDQ is the dependent variable, and time and first contact health provider will be entered as fixed factors. The exact handling of time as a continuous or categorical variable depends on the distribution. Previous studies have found that the clinical course of a back episode is not linear over time (3, 25, 26). It is therefore reasonable to believe that time will have to be treated as a categorical variable, or by introducing a quadratic term, depending on its distribution. Choice of covariance matrix is dependent on data structure. Interaction between first contact health provider and time will be analysed.

Secondary aim, prognostic value of number and severity of comorbidities on the course of back-related disability:

We will fit separate models for count of comorbidity (SCQ part 1, 0-15 scale) and count and severity of comorbidity (full SCQ, 0-45). The steps are outlined below:

1. The univariate association between SCQ and RMDQ over time will be assessed with a mixed model for repeated measures. An interaction term for SCQ*time will be tested, and kept if statistically significant. We will present the crude regression estimates from this analysis.
2. A mixed model with all the covariates from Table 1 and RMDQ over time will be fitted. From this model, r^2 will be presented as a measure of prognostic value.
3. SCQ will be added to the model from step 2. The adjusted regression estimate, and the r^2 -change from step 2 to step 3 will be presented.

Previous studies have found a linear relationship between number and severity of comorbidity and disability (7, 27). Linearity between SCQ and RMDQ will be assessed with a scatter-plot. In case of non-linearity between SCQ and RMDQ comorbidity count and disability score, the following alternatives will be discussed (24, 28):

- Categorization of SCQ
- Transformation (logarithmic or cubic) of SCQ
- Fractional polynomials for SCQ
- Spline functions for SCQ

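### The latent-class course SAP compares only a random intercept and a random slope; if baseline pain correlates less with follow-up than follow-ups do with each other, standard errors for change from baseline are misstated

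*Combined protocol and SAP*

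**What the plan says.** The plan is the SAP on the 2-year clinical course of pain intensity and symptom satisfaction for latent classes (dated 21.02.2024).

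- **Mean model** (section 4, Statistical analysis): it contains "the main effect of the classes and the follow-up time points, in addition to the interaction between the two (classes x follow-up"). Table 2 lists the time points as categories with baseline as reference.
- **Covariance** (same section): "We will use a subject-specific random intercept". Other residual matrices appear only in the general description of what mixed models can do. None is selected.
- **Model comparison** (Model estimation and selection): log likelihood and/or AIC will be used "to determine whether the inclusion of a random slope is necessary and improves the model fit". The time scale of that slope is not given.
- **Reporting**: "crude and adjusted beta coefficients (B) with 95% confidence intervals (CI"), with statistical significance shown in bold in Table 2.
- **Data**: follow-up questionnaires "at 3 months, 6 months, 12 months, and 24 months". The number with complete answers for the pain analysis, from baseline to 24 months, "was 358, 306, 293, 281, and 248, respectively". Missing values are not imputed.

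No unstructured covariance, visit-specific variance or robust standard error is planned. The SAP on one-year disability and comorbidity, for the same cohort, leaves the matter open under its primary aim: "Choice of covariance matrix is dependent on data structure".

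**The concern.** A random intercept implies one variance for all five visits and one correlation for every pair of visits. Baseline is not like the other visits. Patients enter when they seek care for a new episode, and the SAP's own Background describes back pain as a condition of flare-ups and partial recovery. The disability SAP cites modest improvement up to three months and little afterwards, which suggests a break after baseline rather than steady drift. The four classes are also built partly from baseline NRS, so conditioning on class may remove some of the baseline variance and some of its correlation with later scores.

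If the baseline-to-follow-up correlation is below the correlation among follow-ups, the random intercept averages the two. It then credits change from baseline with more correlation than it has. Table 2's time and class-by-time rows are all such changes, so the confidence intervals and bolded p-values that answer the primary aim depend on this choice.

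**Working it through.** The plan states no SD, correlation, standard error or power for this analysis, so there is no figure to reproduce.

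**Inputs.** From the SAP: five visits, baseline as reference, NRS counts 358/306/293/281/248. Assumed: baseline SD s0 = 2.0-2.2, follow-up SD s1 = 2.2-2.5, baseline-to-follow-up correlation r0 = 0.3-0.5, follow-up-to-follow-up correlation r1 = 0.6-0.7.

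**Formula (complete data, time categorical).** Of the 10 visit pairs, 4 involve baseline and 6 do not. The closest random-intercept covariance has

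- mean variance v = (s0² + 4·s1²)/5
- mean covariance c = (4·r0·s0·s1 + 6·r1·s1²)/10

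The model's variance for a change from baseline is proportional to 2(v − c). The true one is proportional to s0² + s1² − 2·r0·s0·s1. The SE ratio is the square root of the first over the second, and the error of a nominal 5% test is 2Φ(−1.96 × ratio). With equal SDs the ratio reduces to √((1 − ρ)/(1 − r0)), where ρ = (4·r0 + 6·r1)/10.

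**Worst corner** (2.2/2.2; 0.3/0.7): ρ = (1.2 + 4.2)/10 = 0.54. Ratio = √(0.46/0.70) = 0.81, error 11.2%.

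**Best corner** (2.0/2.5; 0.5/0.6): v = 29/5 = 5.80, c = (10 + 22.5)/10 = 3.25. Ratio = √(5.10/5.25) = 0.986, error 5.3%.

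| s0 / s1 | r0 / r1 | SE ratio | Test error |
|---|---|---|---|
| equal | 0.3 / 0.3 | 1.00 | 5.0% |
| equal | 0.5 / 0.6 | 0.94 | 6.6% |
| equal | 0.3 / 0.6 | 0.86 | 9.1% |
| equal | 0.3 / 0.7 | 0.81 | 11.2% |
| 2.0 / 2.4 | 0.5 / 0.6 | 0.978 | 5.5% |
| 2.0 / 2.5 | 0.5 / 0.6 | 0.986 | 5.3% |
| 1.5 / 2.4 (outside the assumed range) | 0.5 / 0.6 | 1.013 | 4.7% |

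For the last row: v = 25.29/5 = 5.058, c = (7.2 + 20.736)/10 = 2.794. Ratio = √(4.529/4.41) = 1.013, slightly conservative.

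**Adding a random slope on months.** The range hardly moves. At the best corner the four follow-up contrasts have ratios of 0.981-0.996, against 0.986 with the intercept alone.

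**With the plan's NRS counts** (monotone dropout assumed; equal SDs; 0.3/0.6), large-sample fits give 95% interval coverage at 3 months of 91.2% with the random intercept and 91.2% with the slope on months. With that slope, coverage at 24 months is 92.4%. In 400 simulated data sets AIC chose the slope in 77%. Coverage after that choice was 91.8/92.5/93.8/92.2% at 3/6/12/24 months, with Monte Carlo error of about 1 to 1.5 points.

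**Would AIC reveal the problem?** In the same scenario the expected AIC of an unstructured covariance is about 62 points better than the random intercept, while the slope on months gains only 2.6. If all correlations are equal, unstructured is 26 points worse, which is 2 × (15 − 2) parameters. The criterion would separate the two situations, but the plan does not put the unstructured model forward.

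The same ratios apply to class-by-time terms if the covariance is common and dropout is similar across classes.

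**The case against.** The strongest reply is that nothing in the documents shows the correlation pattern. A reader might infer that the intervals are too narrow as a matter of fact, or that a low baseline correlation is enough to make them so. Neither follows. At 0.3 throughout, the planned model is correct. The condition is a baseline correlation lower than that among follow-ups.

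The documents also contain a reason for a smaller error. Classes built partly from baseline NRS may shrink the within-class baseline SD, and that moves the ratio back towards 1 or just above it. With a slope on months, the 24-month interval can also be near nominal or slightly wide. Because the slope's time scale is unstated, a slope on a post-baseline indicator would not be excluded, and with equal SDs that would fit the pattern exactly. But the plan does not describe one. All of this stands, and it makes the point conditional.

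A reader might also infer biased means, since 248/358 = 69% of baseline patients remain at 24 months and there is no imputation. The checks do not support this. With dropout depending on the previous score, at the plan's counts, the shift was about 0.05 NRS points or less.

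That the aim is exploratory does not remove the point, because intervals and bolded p-values will still be reported.

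**Conclusion.** The point holds conditionally, for NRS. The plan compares two covariance structures, and neither (with a slope linear in time) can represent a baseline that correlates less with the follow-ups than they do with each other. Under the stated assumptions the random-intercept standard error for change from baseline is about 0.81-0.99 of the true one, so nominal 5% tests have about 5-11% error. A linear random slope gives nearly the same range. The error is nil if variances and correlations are equal, and its sign can reverse slightly if the baseline SD is much smaller. No claim of biased means is made.

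For PASS the point cannot be settled yet. The Outcome measure section lists PASS only at the four follow-ups, while the Sample size section gives a baseline count of 365 and Table 2 has a baseline reference row. These must be reconciled first.

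**What to change.** Keep time categorical and prespecify an unstructured 5×5 residual covariance, in place of the random intercept, as the primary model for NRS. At minimum, add it to the planned AIC comparison, which can otherwise stay. State the time scale of any random slope. If the unstructured model does not converge, use the random-intercept model with robust standard errors clustered on patient. Apply the same to PASS once its baseline measurement is clarified.

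The change is one line in the SAP and one in the code. It costs 15 covariance parameters (5 variances, 10 covariances) instead of 2 for the random intercept or 4 with a slope, which is small for 358 patients. Intervals will be slightly wider in places. If the planned model is in fact right, little precision is lost.
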